**Table 1 Objectives and Corresponding Endpoints**

Objective	Endpoints
Primary Objectives	

 
To investigate the effect of esomeprazole on the PK of balovaptan following a single oral dose of balovaptan in the fasted state
 
To investigate the effect of a high-fat meal compared to the fasted state on the PK of balovaptan following a single oral dose of balovaptan
 
	
 
Plasma concentrations of balovaptan
 
Derived plasma PK parameters for balovaptan
 

Secondary Objectives	

 
To investigate the effect of esomeprazole on the PK of M2 (as appropriate) and M3 following a single oral dose of balovaptan in the fasted state
 
To investigate the effect of a high-fat meal compared to the fasted state on the PK of M2 (as appropriate) and M3 following a single oral dose of balovaptan
 
To measure the PK of esomeprazole following 5 once daily dosing of esomeprazole
 
	
 
Plasma concentrations of M2 and M3
 
Derived plasma PK parameters for M2 and M3
 
Plasma concentrations of esomeprazole
 
Derived plasma PK parameters for esomeprazole
 

Objective	Endpoints

 
To investigate the safety and tolerability of a single 20 mg oral dose of balovaptan alone or in combination with esomeprazole in healthy subjects
 
	
 
Incidence and severity of AEs, incidence of SAEs, nonserious AESIs, and AEs leading to treatment withdrawal
 
Results of vital signs, 12-lead ECGs, physical examinations, and clinical laboratory tests
 

Exploratory Objectives	

 
To explore the effect of genetic variations in genes associated with drug ADME and transport on the PK and/or safety profile of balovaptan.
 
	
 
Genotyping data for study subjects. Data will be reported separately if analysis is conducted
 

ADME=absorption, distribution, metabolism, excretion; AE=adverse event; AESI=adverse event of special interest; ECG=electrocardiogram; PK=pharmacokinetics; SAE=serious adverse event;

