### **3.3 RATIONALE FOR STUDY DESIGN**

This study is designed to evaluate the effect of food and modification of gastric pH by esomeprazole on the PK of balovaptan, with the highest dose strength of the final formulation of balovaptan that may be used in pivotal studies. The PK parameters of balovaptan administered fasted with or without administration of esomeprazole, a gastric pH modifier, or balovaptan administered following a high-fat, high-calorie meal, will be compared. A crossover design was chosen to allow for within-subject assessments, minimizing the impact of variability across subjects on the planned analyses. An open-label study was considered appropriate because of the objective nature of the PK measures.

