### **6.1 DETERMINATION OF SAMPLE SIZE**

Sixteen subjects will be enrolled with the target of at least 12 evaluable subjects available for the final PK analysis. Considering the observed residual CV% for AUC0-inf from Study WP40038 of approximately 14%, with 12 subjects the 90% CI would be obtained by dividing/multiplying the ratio estimate by a factor of 1.11.

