The effect of food on the PK of balovaptan will be assessed using the ratio and 90% CIs of the geometric least squares (LS) means of the plasma PK parameters  $C_{max}$  and  $AUC_{0-inf}$  for balovaptan. A linear mixed model with fixed effects for treatment, period, sequence, and a random effect for subject nested in sequence will be used on the natural log-transformed parameters. Point estimates on the natural log scale will be exponentiated to obtain point estimates on the original scale of measurement. Geometric LS means will be provided for each treatment. Food had no relevant effect on the overall exposure of the capsule formulation of balovaptan but  $T_{max}$  was shifted from 1 hour after dosing under fasted conditions to approximately 3 hours in fed conditions.

The effect of esomeprazole on the PK of balovaptan will be assessed using the ratio and 90% CIs of the geometric LS means of the plasma PK parameters:  $C_{max}$  and  $AUC_{0-inf}$  for balovaptan. A linear mixed model with a fixed effect for treatment and a random effect for subject will be used on the natural log-transformed parameters. Point estimates on the natural log scale will be exponentiated to obtain point estimates on the original scale of measurement. LS geometric means will be provided for each treatment.

In all comparisons, balovaptan under fasted conditions will be used as the reference. No adjustments will be made for multiplicity.

PK parameters will be estimated using standard noncompartmental methods.

Additional PK analyses maybe be conducted as appropriate for balovaptan, M2, and M3.

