## Appendix 1: Schedule of Activities

	Scr	Period 1								Period 2								Period 3								F/U
	D -28 to -2	D -1	D 1	D 2	D 3 & 4	D 5	D 7	D 9	w/o	D -1	D1	D 2	D 3 & 4	D 5	D 7	D 9	D10 to D12	D 13 a	D -1 a	D 1	D 2	D 3 & 4	D 5	D 7	D 9	D16 ±2 or ET
Biochemistry	X	X				X				X				X		X			X				X			X
Urinalysis	X	X																								X
Coagulation	X	X																								X
Urine drug and alcohol screen l	X	X								X					X											
Serology	X																									
Pregnancy test m	X	X								X					X											X
FSH n	X																									
Genotyping sample		X																								
Adverse event monitoring	X	X	X	X	X	X	X	X		X	X	X	X	X	X	X	X	X	X	X	X	X	X	X	X	X

ET=early termination; F/U= follow-up; FSH=follicle-stimulating hormone; w/o=washout

- Day 13 of Period 2 is Day -1 of Period 3.
- Balovaptan will be administered following a high-fat, high-calorie meal (Treatment A) or after a ≥ 10 h fast (Treatments B and C). Subjects should fast for 4 hours after balovaptan administration and refrain from drinking for 1 hour prior to and 1 hour post dose.
- Esomeprazole will be administered 1 hour prior to balovaptan.
- Standardized meals will be provided at approximately 4 and 8 hours post-balovaptan dosing in each treatment period
- Samples at predose, and at 0.25, 0.5, 1, 1.5, 2, 2.5, 3, 3.5, 4, 5, 6, 8, 12, 16, 24, 36, 48, 72, 96, 144, and 192 hours post dose
- Samples at predose, 0.25, 0.5, 1, 1.5, 2, 3, 4, 6, 8 hours post dose of esomeprazole
- Height, weight, and BMI calculation at screening; only weight at all follow-up.
- Safety ECG will be performed in triplicate at Screening and on Day -1 of each period; at all other time points single ECGs will be performed.
- Body temperature and respiratory rate will be measured at Screening and Day -1 of each period only.
- Orthostatic challenge testing will be performed at screening.
- On Day 1, vital signs measurements will be performed at 1 hour post dose.
- Drugs of abuse (amphetamines [including ecstasy], barbiturates, benzodiazepines, cannabinoids, cocaine, cotinine, opiates, methamphetamines, and methadone).
- Serum pregnancy test performed on all female subjects at Screening and Day -1 of each treatment period (Day 13 of Period 2 is Day -1 of Period 3) and at follow-up.
- In postmenopausal women to confirm menopause

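### Tmax is left to listings and per-treatment summaries; a paired difference with a 90% CI would be a cheap addition to Section 6.6

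*Combined protocol and SAP*

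**What the plan says.** Both primary objectives in Table 1 concern effects on balovaptan PK, and the endpoints include "Derived plasma PK parameters for balovaptan". Section 3.3 says the crossover was chosen for within-subject assessment. It also names what is to be compared: "The PK parameters of balovaptan administered fasted with or without administration of esomeprazole", together with those after the high-fat meal.

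Section 6.6 lists Tmax and Tlag among the parameters to be estimated. Individual derived values are listed, and each treatment gets summary statistics that include medians and ranges. The inferential part is narrower. Each effect "will be assessed using the ratio and 90% CIs of the geometric least squares (LS) means" for Cmax and AUC0-inf. The food paragraph then says that food had no relevant effect on overall exposure with the capsule, but that Tmax "was shifted from 1 hour after dosing under fasted conditions to approximately 3 hours in fed conditions".

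Two provisions leave room for more. Section 6 promises a separate SAP before database lock, which is not among the documents. Section 6.6 allows further PK analyses as appropriate. Neither names a Tmax comparison.

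**The concern.** The plan reports a timing effect of food in the same paragraph that defines the food comparison, and then gives no estimator for that effect. Medians and ranges by treatment do not use the pairing that the crossover provides. For food, they also make no use of the randomised order of A and B to adjust for period.

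At stake is how a delay would be reported. The study report would show two medians with ranges, and the reader could not say how long the within-subject delay is or how well it is known. This matters more because the size of any shift with the 20-mg dispersible tablet is uncertain. Section 1.2.1.1 gives median Tmax of 1 to 4.5 h fasted after single doses and 3 to 4 h fed after multiple dosing. Those ranges overlap.

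**Working it through.** **1. The plan's own precision figure.** Section 6.1 states "Sixteen subjects will be enrolled with the target of at least 12 evaluable subjects available for the final PK analysis". It takes the residual CV for AUC0-inf "from Study WP40038 of approximately 14"% and concludes that "with 12 subjects the 90% CI would be obtained by dividing/multiplying the ratio estimate by a factor of 1.11".

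- Log-scale SD: s = sqrt(ln(1 + 0.14²)) = 0.1393
- Factor: exp(t(0.95, 10 df) × s × sqrt(2/12)) = exp(1.8125 × 0.1393 × 0.4082) = exp(0.1031) = 1.109, which rounds to 1.11

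The figure reproduces. It concerns AUC0-inf only and says nothing about Tmax.

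**2. Can 12 pairs give a 90% interval for a Tmax difference?**

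- Signed-rank interval: 12 pairs give 12 × 13 / 2 = 78 Walsh averages. The limits are the 18th smallest and 18th largest. P(W ≤ 17) = 0.0461, so exact coverage is 1 − 2 × 0.0461 = 90.8%.
- Two-sequence rank interval, assuming 6 subjects per sequence: of the C(12,6) = 924 arrangements, 1+1+2+3+5+7+11+13 = 43 have a Mann-Whitney statistic of 7 or less. Coverage is 1 − 2 × 43/924 = 90.7%.

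Ties from the sampling grid make both coverages approximate.

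**3. How precise would it be?** The documents give no Tmax variability, so every SD here is an assumption. Lognormal Tmax values for 12 pairs were moved to the nearest time on the Appendix 1 grid ("0.25, 0.5, 1, 1.5, 2, 2.5, 3, 3.5, 4, 5, 6, 8, 12" h and later). The 90% signed-rank interval was then computed. The first two rows draw the two periods independently; the last three add a shared subject effect with log-SD 0.3.

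| True Tmax, fasted to fed | Log-SD fasted / fed | Interval excludes zero | Median full width |
|---|---|---|---|
| 1.2 h to 3 h | 0.5 / 0.4 | about 99% | 1.5 h |
| 2 h to 3 h | 0.5 / 0.4 | about 46% | 1.75 h |
| 1 h to 3 h | 0.3 / 0.3 | about 100% | about 1.2 h |
| 1 h to 3 h | 0.5 / 0.5 | about 99.9% | about 2.0 h |
| 1 h to 3 h | 0.7 / 0.7 | about 90% | about 2.9 h |

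For a shift from 2.5 h to 3 h with log-SDs 0.5 and 0.4, exclusion falls to about 12%. With log-SD 0.7 in both arms, widths are about 2.6 to 3.5 h for shifts to 3 h from 1.2, 2 or 2.5 h. These simulations use the signed-rank interval. The two-sequence interval proposed for food was not simulated.

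**4. Period.** In the randomised part, the Period 1 minus Period 2 difference estimates (A − B) plus a period effect in sequence ABC, and (B − A) plus the same period effect in BAC. Subtracting one sequence from the other leaves 2(A − B), so half the rank-based shift is free of an additive period effect. For C − B no such device exists: every subject receives C in Period 3, and B in Period 1 or 2.

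**The case against.** The best case for the plan as written has five parts.

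- **Timing is described.** A reader might infer that the trial would learn nothing about absorption timing. The documents do not support that. Tmax and Tlag are derived, individual values and profiles are shown, and medians and ranges are tabulated. In the 1.2 h to 3 h scenario the raw medians differed in the right direction in essentially every simulated trial. What is missing is the paired estimate and its precision.
- **Cmax is modelled.** It is tempting to say that the models omit the one parameter food is known to change. Section 3.3.1.1 says that the earlier food effect was, in particular, a lower Cmax. Cmax is in both formal contrasts and partly reflects absorption rate, although it does not measure a delay in hours.
- **No esomeprazole delay is predicted.** The protocol says that pH-dependent solubility may affect absorption, and expects either no effect or reduced exposure. A Tmax delay with esomeprazole is a possibility that it does not raise.
- **High power is not assured.** The 1 h to 3 h shift comes from the capsule, and smaller shifts would often leave an interval that includes zero. This stands, but an interval is useful because it shows what the data cannot settle.
- **Room is left for more.** The later SAP or the optional analyses may add the comparison. Nothing available pre-specifies it.

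It is also fair that equal allocation to ABC and BAC cancels additive period effects in the treatment means while the sequences stay balanced. That protection does not carry over exactly to medians, or to unequal dropout.

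**Conclusion.** The point holds as a cheap improvement of minor severity. Section 6.6 gives no within-subject Tmax estimate or interval for either contrast, in a crossover chosen for within-subject assessment and with an earlier Tmax shift on record. The primary parameters, their conclusions and the sample size are untouched.

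The paired analysis is feasible at the planned 12 evaluable subjects. Its yield depends on the true shift and on Tmax variability, neither of which the documents give for this tablet. Under the assumptions above, the chance that the interval excludes zero runs from about 99% (1.2 h to 3 h) through about 46% (2 h to 3 h) to about 12% (2.5 h to 3 h). The esomeprazole interval would carry the same confounding with period as the planned Cmax and AUC0-inf comparison.

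**What to change.** In Section 6.6 and the SAP, add a supportive analysis of the within-subject difference in untransformed Tmax, based on actual sampling times (already recorded under Timing of Study Assessments). Report the Hodges-Lehmann median difference with a 90% CI for each contrast:

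- **A − B:** the two-sequence rank method on Period 1 minus Period 2 differences, with the between-sequence shift halved.
- **C − B:** the signed-rank interval on paired differences, with a statement that a treatment effect cannot be separated from a period effect because C is always given in Period 3.

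Keep Cmax and AUC0-inf as the primary parameters. The cost is a few lines of text, one extra table and one more unadjusted interval per contrast, in line with the plan's decision not to adjust for multiplicity. No extra samples or subjects are needed.

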### 3. STUDY DESIGN

#### 3.1 DESCRIPTION OF THE STUDY

This will be a single-center, part-randomized, open-label, single-dose, 3-period crossover study to investigate the effect of food and of esomeprazole on the PK of balovaptan in healthy volunteers.

Screening will be conducted between Day -28 and Day -2.

In Period 1, eligible subjects will be admitted to the clinical research unit (CRU) on Day -1 (the day prior to balovaptan dosing on Day 1) and will remain confined in the CRU until discharge on the morning of Day 5.

In Period 2, subjects will be re-admitted to the CRU on Day -1 (the day prior to balovaptan dosing on Day 1) and will remain confined in the CRU until discharge on the morning of Day 5.

In Period 3, subjects will return to the CRU for re-admission 5 days prior to administration of balovaptan (Day 9 of Period 2) to begin esomeprazole dosing. Esomeprazole will be dosed for 6 days: for 4 days prior to co-administration with balovaptan on Day 1 of Period 3, plus an additional dose on Day 2. Subjects will be discharged on Day 5.

In each period, following discharge from the CRU on Day 5, subjects will return to the CRU on Day 7 and Day 9 for further PK sampling.

There will be a washout of at least 12 days and up to 21 days between administrations of balovaptan. Thus, re-admission for Period 2 may be between 3 to 12 days after Day 9 of Period 1, and re-admission for Period 3 will be on Day 9 of Period 2.

Subjects will be randomized to 1 of 2 treatment sequences (ABC or BAC) on Day 1 of Period 1, with the treatments being as follows:

[figure not shown]
- Treatment A: 20 mg balovaptan administered as a single oral dose following consumption of high-fat, high-calorie meal
- Treatment B: 20 mg balovaptan administered as a single oral dose following a  $\geq 10$ -hour fast
- Treatment C: 40 mg esomeprazole administered once daily for 6 days and with a single oral dose of balovaptan 20 mg in the fasted state 1 hour after the fifth esomeprazole dose

During treatment periods 1 and 2, subjects will receive each of Treatment A or B, according to the randomization schedule. All subjects will receive Treatment C in Treatment Period 3.

Subjects will return for a follow-up visit on Day 16  $\pm$  2 of Period 3. Assessments during the study will be conducted according to the schedule of assessments ([Appendix 1](#)).

[Figure 1](#) presents an overview of the study design.

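### Does leaving period out of the esomeprazole model, when esomeprazole is always given in Period 3, call for a different analysis?

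*Combined protocol and SAP*

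**What the plan says.** Section 3.1 describes the allocation: "Subjects will be randomized to 1 of 2 treatment sequences (ABC or BAC) on Day 1 of Period 1". A is balovaptan after a high-fat meal, B is balovaptan fasted, and C is balovaptan fasted with esomeprazole. Only the A/B order is randomised: "All subjects will receive Treatment C in Treatment Period 3".

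Table 1 lists two primary objectives. One of them is: "To investigate the effect of esomeprazole on the PK of balovaptan following a single oral dose of balovaptan in the fasted state". Section 6.6 fixes the comparator: "In all comparisons, balovaptan under fasted conditions will be used as the reference". The esomeprazole contrast is therefore C against B.

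Section 6.6 gives the two contrasts different models. Food (A against B): "A linear mixed model with fixed effects for treatment, period, sequence, and a random effect for subject nested in sequence". Esomeprazole (C against B): "A linear mixed model with a fixed effect for treatment and a random effect for subject". The output for esomeprazole is "the ratio and 90% CIs of the geometric LS means of the plasma PK parameters". No equivalence bounds or interaction decision rule are stated.

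Section 6.1 bases precision on a residual CV for AUC0-inf "from Study WP40038 of approximately 14%, with 12 subjects", giving a CI factor of 1.11. Section 6 defers further detail to a separate SAP, to be finalised before database lock, which is not among the documents.

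**The concern.** B is given in Period 1 (sequence BAC) or Period 2 (sequence ABC), and C only in Period 3. The C/B ratio is thus the esomeprazole effect multiplied by whatever changes between the earlier periods and the last one. The plan adjusts for period where order is randomised and omits it where order is not, which reads like an oversight. Neither the design rationale (Section 3.3) nor Section 6.6 states that no period effect is assumed.

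Period 3 is also visibly different. Subjects are admitted 5 days before balovaptan instead of 1 day, and two balovaptan doses have gone before. Section 3.3.1.1 expects esomeprazole either to do nothing or to lower exposure, so upward drift could hide a real reduction: a true ratio of 0.85 with a +10% Period 3 shift would be estimated at about 0.85 × 1.10 = 0.94. At stake would be one of the two primary conclusions, with a 90% CI that covers random error only.

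**Working it through.** **Inputs.** CV 14% and n = 12 (Section 6.1); sequences ABC and BAC in equal proportions (Sections 3.1 and 4.2), taken as 6 + 6; washout of at least 12 days (Section 3.1); half-life about 46 h (Section 1.2.1.1). Drift sizes are assumed, because the documents give none.

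**1. The plan's own figure.** s = √ln(1 + 0.14²) = 0.1393. SE of a log ratio = 0.1393 × √(2/12) = 0.0569. With t(0.95, 10) = 1.812 the factor is exp(1.812 × 0.0569) = 1.109; with t(0.95, 11) = 1.796 it is 1.108. Both round to the stated 1.11.

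**2. What the planned model estimates.** The least-squares weights of C minus B on the effects of Periods 1, 2 and 3 are −0.5, −0.5 and +1. A shift confined to Period 3 enters one-for-one. Under linear drift, B sits on average 1.5 periods before C.

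**3. Size if drift existed.** Bias = 1.5 × ln(1 + d). Coverage of the nominal 90% CI comes from the noncentral t with 11 df and noncentrality bias/SE.

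| Assumed drift per period | C/B ratio multiplied by | Coverage |
|---|---|---|
| 1% | 1.015 | 89% |
| 2% | 1.030 | 86% |
| 3% | 1.045 | 81% |
| 5% | 1.076 | 67% |
| 7% | 1.107 | 49% |

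**4. Could period simply be added, as in the food model?** No. With subject, treatment and a three-level period factor on the A, B and C data, the design matrix has 16 columns and rank 15. With B and C data only, it has 15 columns and rank 14. C minus B is non-estimable in both. A minus B and Period 2 minus Period 1 remain estimable because A and B swap places. The plan therefore uses the period factor in the one contrast where the design supports it.

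**5. Could a restricted period term help?** On the A, B and C data:

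| Model | Weights on Periods 1, 2, 3 | Linear drift left (periods) | Period 3-only shift left | SE | CI factor |
|---|---|---|---|---|---|
| Planned, no period (11 df) | −0.5, −0.5, +1 | 1.5 | all | 0.0569 | 1.108 |
| Period 1 vs later (21 df) | 0, −1, +1 | 1.0 | all | 0.0636 | 1.116 |
| Linear period (21 df) | +1, −2, +1 | 0 | all | 0.1025 | 1.193 |

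The indicator assumes that Period 3 equals Period 2 and keeps 1.0/1.5 = two-thirds of a linear drift. The linear term is right only if drift is exactly linear. Neither touches a shift confined to Period 3.

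**6. Cost of requiring agreement with the linear model.** As an illustration only, take bounds of 0.80 to 1.25 (the plan states none) and a true ratio of 1. The chance that the 90% CI falls inside is about 96% with SE 0.0569 and 11 df, and about 36% with SE 0.1025 and 21 df.

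**7. Would the Period 2/Period 1 ratio reveal drift?** The food model estimates it with SE 0.0569 and a CI factor of about 1.11. A true 5% drift per period would push that 90% CI off 1 only about 21% of the time.

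**8. Carry-over.** 12 days × 24 h / 46 h = 6.3 half-lives; 2^(−6.3) is about 1.3% remaining.

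**The case for a change.** The strongest case for acting is that the C/B contrast is not randomised and the text never says so in those terms. The SAP is still open, and the randomised A/B part carries information on drift that the esomeprazole analysis leaves unused. Both restricted models can be fitted, and the Period 1 indicator costs almost nothing (factor 1.116 against 1.108). Reporting them beside the planned result would show whether the conclusion depends on the no-drift assumption.

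The structural point stands in full, and so does the observation that the assumption is unstated. The case for extra required models does not. Agreement between the planned and restricted fits would give false comfort, because all three pass a Period 3-only shift through unchanged. The most concrete Period 3 difference, the longer confinement, exists to deliver the esomeprazole lead-in. It would come with C in whichever period C was given, so no period term could separate the two. Making conclusions conditional on the linear model would discard much of the precision the study was sized for, and would gate a decision rule the plan does not have. The Period 2/Period 1 ratio is already a by-product of the food model, and Section 6.6 leaves room for additional PK analyses, so an analyst can show it as background without any change to the plan.

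**Conclusion.** No change to the plan. The esomeprazole contrast is a fixed-sequence comparison and its CI is valid only if Period 3 does not differ from Periods 1-2 for reasons other than treatment. That follows from the design, which Section 3.1 discloses, and it cannot be repaired by modelling: true separation would need C in more than one period or an outside assumption.

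The possible bias is real in principle: 3% to 7% drift per period would move the ratio by 4.5% to 10.7%, against a CI factor of 1.11. Those drift values are assumed. Comparisons are within subject at one centre, Day 1 meals are standardised, and carry-over is about 1.3%, so nothing in the documents points to drift of that size. At 1% to 2% per period, coverage stays at 86% to 89%. The sizes use the AUC0-inf CV and 12 evaluable subjects; the documents give no CV for Cmax.

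Leaving period out is a fair trade-off: one simple, precise estimate under a visible assumption, instead of less precise estimates under different assumptions that are no easier to test. A careful report would name the fixed sequence as a limitation and could show the Period 2/Period 1 ratio as indirect context. That alters no estimate or interval.
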